2. OBJECTIVES

Primary Objective: To determine the efficacy of DPCP ointment for the treatment of alopecia areata.

Secondary Objectives: 1) To assess the safety of DPCP ointment in alopecia areata subjects.
2) To determine the best starting dose range for future studies

Exploratory Aims: 1) To evaluate the association between cytokine and keratin profiles, Cytomegalovirus UL16 Binding Protein (ULBP) expression and hair regrowth.

3. STUDY DESIGN

- The products to be evaluated are 0.4% DPCP and four strengths of DPCP ointment (0.04, 0.08, 0.12, 0.2%) (Add preparation) Four dose concentrations of DPCP ointment (0.04, 0.08, 0.12, 0.2%) will be prepared through dilutions of 0.4% DPCP Ointment (applied to

the inner aspect of the left upper thigh) and these will be applied sequentially starting with the lowest concentration and, if no sensitization is attained, sensitization to the next lowest dose will be attempted. This will be repeated until either the participant has a reaction and that concentration will be their dose for the duration of the study or until all concentrations have been unsuccessful in causing a reaction. If this is the case, the participant will be discontinued from the study. (“Dose Determination Visit”; 10-14 days after the Sensitization Visit)

For sensitization, 0.05 mL of the 0.4% concentration will be applied topically to the right upper inner arm. If sensitization is not attained after 10 to 14 days, the procedure will be repeated once. After sensitization is established, the lowest treatment dose will be applied to the inner aspect of the upper left thigh. If sufficient sensitization is not attained, the next lowest treatment dose will be applied, etc, until sensitization is attained. If no sensitization is attained to any of the 4 concentrations, the participant will be discontinued from the study. The treatment dose will be selected based on lowest concentration of DPCP that causes minimal reaction. This treatment dose will be used throughout the study. The treatment phase of the study will consist of twice-weekly applications of 0.75-1 g DPCP ointment to the entirety of the scalp. Every four weeks during treatment, the investigator will assess hair loss as described below:

- 1) Efficacy will be assessed as follows:
 - a. Severity of Alopecia Tool (SALT) Score: Percentage of hair loss on the scalp will be determined using the SALT score, a global alopecia areata severity score based on scalp hair loss.^{20,21} The SALT score is calculated by visually examining *four* discrete areas of the scalp, measuring the percentage of terminal hair loss in each area, and then totaling the results (See Appendix B).
 - b. Scalp Photography.
 - c. Hair Pull Tests (positive or negative).
- 2) Safety will be assessed by monitoring side effects at each visit and recording adverse events for each subject on the Adverse Event Report (Appendix C). Adverse events will be tracked for each subject from the time of the first sensitization does application of the drug until the subject completes the study. Adverse events will be assessed for severity by the investigator and graded on a four-point scale (mild, moderate, severe, or life-threatening). Serious adverse events will also be recorded on the Severe Adverse Event Report (Appendix D), and the study drug manufacturer and the U of MN IRB, and the FDA will be notified. Skin reaction scores will be recorded during the sensitization assessment (Appendix I) to monitor reactions, and may constitute an adverse event based on severity of reaction.
- 3) Molecular and immunological characterization of the Alopecia Areata disease process and how it changes throughout the course of treatment with DPCP will be achieved through mRNA expression profiling in blood and scalp biopsy specimens, and histopathology analyses.
- 4) Molecular predictors of positive and negative response to DPCP treatment will be identified through expression profiling targeted to mRNA transcripts for cytokines, T cell

subsets, and hair keratins in scalp biopsy specimens. Peripheral blood mononuclear cells will be frozen and also serum frozen for future studies looking downstream for possible changes with DPCP in T-cell activation markers or circulating cytokines such as gamma-interferon, IL-13, IL-17, and/or an increase in Tregs (CD25+/CD127- population or Foxp3+ population). This will not need to happen in blood if all the changes however are found to be happening in skin/scalp.

3.1 Study Design

This is an open labeled study to determine the response and characteristics, safety and efficacy, of the proprietary DPCP ointment composition as a topical immunotherapeutic agent for the treatment of extensive Alopecia Areata. The products to be evaluated are 0.4% DPCP and four strengths of DPCP ointment (0.04, 0.08, 0.12, 0.2%), with each dose determined for every participant individually.

Up to 10 (minimum of 6) subjects with diagnosed extensive alopecia areata (76%-99% scalp hair loss as determined by the SALT score; see Appendix B, Part I) that are eligible for DPCP treatments will be consented and enrolled in the study. Patients with alopecia areata will be recruited from the new and current patient population seen in the University of Minnesota Medical Center Dermatology Clinics as well as through partnership with the National Alopecia Areata Foundation Clinical Trials Network. Potential subjects will also be recruited using flyers posted at the University of Minnesota and in surrounding communities. The study may be advertised using various media outlets, including newsletters, campus wide mailings, campus email announcements, the Dermatology department website, and listservs in the Twin Cities area (including the listserv for the Minnesota Alopecia Areata Support Group). All materials used in recruitment will be approved by the Institutional Review Board (IRB) prior to implementation.

There will be a total of 42 scheduled visits, beginning with a screening visit. Subjects will undergo 38 scheduled topical applications of a an ointment formulation of DPCP, including a sensitizing dose of study drug at Day -16, an initial dose determining application at Day -2, followed by a challenge at Day 0, and twice weekly (+/- 2 days) treatment doses from Weeks 1-18. Additional applications of DPCP could include another sensitization visit or additional dose determination visits for the higher concentrations, if necessary. There will be a scalp biopsy collection at baseline (Visit 2, Day -16), and visits for scalp biopsy collection 72-96 hours after the first treatment, and 72-96 hours after \geq 50% hair regrowth or 72-96 hours after application of the final treatment dose. Suture removal will take place during treatment visits or scheduled 7-14 days after each biopsy visit. Several questionnaires and forms will be completed throughout the duration of the study.

Research coordinators will be involved in patient recruitment, contact, and scheduling. The PI and research coordinators will all be involved in the collection, analysis, and reporting of collected data.

All visits will take place either in the M Health Clinical Research Unit (CRU), part of the Clinical and Translational Science Award at the University of Minnesota, or in the LCRU. There are no additional collaborating sites for this study.

Schedule of Visits

Procedure	Visit							
	1 ^a	2 ^b	3 ^c	4 ^d	5	6-40 ^e	41	42 ^f
Informed consent	X							
Screening for eligibility	X							
Blood tests	X					X (1 time at week 12)	X	
Pregnancy test	X					X (1 time a month)	X	
Vital signs	X	X			X	X (1 time a mo.)	X	
Adverse events		X	X	X	X			X
Assessment of hair loss	X		X			X (1 time a month)	X	
Photographs		X	X			X (1 time a month)	X	
Scalp biopsy procedure		X			X	X (if 50% regrowth)	X	
Suture removal				X		X (as needed)		X
Blood draw		X			X	X (if 50% regrowth)	X	
DPCP ointment - sensitizing		X						
DPCP ointment – dose determination for each concentration: 0.04, 0.08, 0.12, 0.20			X					
DPCP ointment - challenge				X				
DPCP ointment - treatment				X	X	X (twice per week For 17 weeks, visit 40 will occur during week 18)		
Study completion								X

- a. Screening visit
- b. Sensitization and baseline sample collection – visit can be repeated if participant not a responder to DPCP the first time. Blood draw and scalp biopsy procedure will only take place if sensitization has occurred and the participant is a responder to DPCP.
- c. Dose determination visit – see following schedule of events for more details.
- d. Challenge visit
- e. Participants will return twice per week for application of the previously selected dose of DPCP. Every four weeks during treatment, the investigator will attend the treatment visit to perform assessments of hair loss.
- f. Suture removal and study completion

Dose Determination visit schedule:

Procedure	Visit			
	3 ¹	3 ²	3 ³	3 ⁴
Adverse events	X	X	X	X
Assessment of hair loss	X			
Photographs	X	X	X	X
DPCP ointment – 0.04%	X			
DPCP ointment – 0.08%		X		
DPCP ointment – 0.12%			X	
DPCP ointment – 0.2%				X

1: DPCP ointment 0.04% concentration is the starting concentration for all participants

2: DPCP ointment 0.08% will only be applied if participant does not have a strong enough response [defined as skin reaction score 1+] to the 0.04% concentration of DPCP. Thus, this visit will begin with an assessment of the sensitization reaction to the 0.04% dose. If there is not a strong enough response, 0.08% concentration DPCP will be applied to a different area of the inner upper left thigh in the same manner as the 0.005% dose. If the participant is a responder to the 0.04% DPCP, patient will proceed to the challenge visit (visit 4) as described above.

3: DPCP ointment 0.12% will only be applied if participant does not have a strong enough response [defined as skin reaction score 1+] to the 0.08% concentration of DPCP. Thus, this visit will begin with an assessment of the sensitization reaction to the 0.08% dose. If there is not a strong enough response, 0.12% concentration DPCP will be applied to a different area of the inner upper left thigh in the same manner as the 0.08% dose. If the participant is a responder to the 0.08% DPCP, patient will proceed to the challenge visit (visit 4) as described above.

4: DPCP ointment 0.2% will only be applied if participant does not have a strong enough response [defined as skin reaction score 1+] to the 0.12% concentration of DPCP. Thus, this visit will begin with an assessment of the sensitization reaction to the 0.12% dose. If there is not a strong enough response, 0.2% concentration DPCP will be applied to a different area of the inner upper left thigh in the same manner as the 0.12% dose. If the participant is a responder to the 0.2% DPCP, patient will proceed to the challenge visit (visit 4) as described above.

Screening Visit

At the screening visit the PI will obtain signed, informed consent and HIPAA approval. Demographic information, weight and vital signs, medical history including concomitant medications will be recorded on the Demographics and Baseline Assessment form (Appendix D). Research personnel will review eligibility with the subject. Lifetime treatment history will also be recorded (Appendix E). A dermatologic exam will be performed to confirm that the extent of alopecia areata is 76-99% hair loss according to the SALT score (Appendix B, Part I). Laboratory tests will be drawn to measure TSH, Hemoglobin (HgB), and Vitamin D level, and thus to reduce the likelihood a common underlying medical problem that impacts hair growth exists prior to study participation. Additional laboratory tests will be drawn as part of safety monitoring as described in section 9.7. Pregnancy test will be administered to all women of childbearing potential, and must be negative to participate. Safety laboratory results will be documented in the subjects' medical record.

An appointment for the sensitization visit will be scheduled with research personnel. If a washout period is required prior to treatment, the subject will return for the sensitization visit at the appropriate time. Otherwise, the research subject may immediately proceed to the sensitization part of the study or may be scheduled at a determined date in the future for the sensitization and baseline sample collection visit described below.

Sensitization and Baseline Sample Collection Visit, Day -16

Inclusion and exclusion criteria will be reviewed again, especially if there was a washout period between the screening and sensitization visits. Interim medical history, concomitant medications, and vital signs will be recorded on a Case Report Form (CRF). Assessments of hair loss, including the SALT score, the Physician Assessment of Alopecia (PAA; Appendix F), and the Subject Hair Loss Assessment (SHLA; Appendix G) will be completed by the physician or subject. Pregnancy test will be administered to all women of childbearing potential, and must be negative to participate. AEs (Appendix C) will be monitored and recorded.

Three 4-mm scalp biopsy samples will be collected from perilesional scalp by a board certified dermatologist knowing that in some patients this site may be by just a few tufts of fibers. One of the three samples will be frozen in OCT for histologic examination and immunohistochemical studies. Those samples will be stored in a -80 degree freezer and batch shipped to [name] and the Laboratory of Investigative Dermatology at Rockefeller University in New York, NY on dry ice every one to two months. A second biopsy sample from each area will be bisected and placed in 10% buffered formalin and Zamboni's fixative for histologic examination and assessment of inflammation and hair follicle differentiation in the Dermatology Laboratory at the University of Minnesota. The third sample from each area will immediately be placed in RNAlater (Qiagen, Valencia, CA) and shipped to the [name] Laboratory in the Laboratory of Investigative Dermatology at Rockefeller University in New York, NY for mRNA-level cytokine analyses.

Peripheral blood samples will be collected by a trained staff member and will include 1 serum separator tube (SST) and 1 PAXgene tube for RNA isolation.

A sensitizing dose of 0.4% DPCP ointment will be applied directly to the inner aspect of the upper right arm. The site where the dose is applied will be marked and photographed as will the extent of scalp disease.

Dose Determination Visit, Day -2 (10 to 14 days post-sensitization)

Assessments of hair loss, including the SALT score and PAA will be completed. AEs (Appendix C) will be monitored and recorded. The sensitization reaction will be recorded by the physician on the Sensitization Assessment form using accepted methods (Appendix I, Part I).⁴² Subjects are considered DTH Responders with skin reaction scores $\geq 2+$ at the inner arm sensitization site. Subjects having skin reaction scores of 0 or 1+ are considered non-responders. In the event the subject has a response that is 4+, this will be considered an AE and recorded as such. Reactions scoring less than 4+ can still be considered an AE at the investigator's discretion.

Non-responders (i.e., subjects who do not have a sensitization response) will receive another sensitization cycle in the manner previously described. If a subject is found to be a non-responder through two cycles of sensitization, they will be discontinued from the study.

A concentration of DPCP 0.04 will be applied by the PI or co-PI in the amount of 50 ul per concentration to the inner aspect of the upper left thigh. The site where the dose is applied will be marked and photographed. The site will be covered with a clear, plastic, waterproof dressing such as Tegaderm. The sensitizing test site is to be discontinued 6-8 hours after application by

the subject removing the Tegaderm and cleansing the test site. The subject will report to the study site in 72 hours. If the patient has a sufficient reaction (DTH skin reaction score of 1+), this will be their treatment dose for the duration of the study and the participant will proceed directly to the challenge visit listed below.

- If no reaction to the DPCP 0.04% preparation, an additional test sensitizing to an alternate site in the inner aspect of the upper left thigh with DPCP 0.08% prepared in the same dilutions as previous dosage. The site where the dose is applied will be marked and photographed. The sensitizing test is to be discontinued 6-8 hours after application by the subject removing the Tegaderm and cleansing the test site. The subject will report to the study site in 72 hours. If the patient has a sufficient reaction [defined as skin reaction score 1+], this will be their treatment dose for the duration of the study and the participant will proceed directly to the challenge visit listed below.
- If no reaction to the DPCP 0.08% preparation, an additional test sensitizing to an alternate site of the inner aspect of the upper left thigh with DPCP 0.12% prepared in the same dilutions as previous dosage. The site where the dose is applied will be marked and photographed. The sensitizing test is to be discontinued 6-8 hours after application by the subject removing the Tegaderm and cleansing the test site. The subject will report to the study site in 72 hours. If the patient has a sufficient reaction [defined as skin reaction score 1+], this will be their treatment dose for the duration of the study and the participant will proceed directly to the challenge visit listed below.
- If no reaction to the DPCP 0.12% preparation, an additional test sensitizing to an alternate site in the inner aspect of the upper left thigh with DPCP 0.2% prepared in the same dilutions as previous dosage. The site where the dose is applied will be marked and photographed. The sensitizing test is to be discontinued 6-8 hours after application by the subject removing the Tegaderm and cleansing the test site. The subjects will return to the study site in 72 hours after test applications. If the patient has a sufficient reaction [defined as skin reaction score 1+], this will be their treatment dose for the duration of the study and the participant will proceed directly to the challenge visit listed below.
- If the subject does not have a reaction to the DPCP 0.2%, they will be discontinued from the study. If a subject is discontinued from DPCP treatment or study participation, they should complete an Early Termination Visit one week after the last drug application.

Challenge Visit, Day 0

AEs (Appendix C) will be monitored and recorded.

This first treatment of the drug of the determined dose will be applied to the entire scalp (0.75-1 g of treatment drug) by the PI or co-PI, both board certified dermatologists. Photographs will be taken prior to the application of the treatment drug to document extent of hair loss.

Post-First Treatment Sample Collection Visit and Second Treatment, Day 3

A visit will occur a minimum of 72-96 hours after the first application of drug in which scalp biopsy and blood specimens will be collected. Vital signs and AEs (Appendix C) will be monitored and recorded. Handling of biopsy and blood specimens will follow the same protocol

as was used at the Sensitization and Baseline Sample Collection Visit, Day -16.

The biopsies taken 3-4 days after application of the first challenge application of DPCP of the determined dose will be approximately 2 inches from the first set of biopsies. These biopsies are being done to define the initial DTH response to DPCP in the scalp. The expectation is that the initial response will differ from a chronic response that becomes more Th1 centered with chronic treatment.

The second treatment with study drug will again be applied by the PI or co-PI. Photographs will be taken to document extent of hair loss.

Treatment Visits, Twice per Week for Weeks 1-18

Subjects will return to Dermatology Clinical Research twice per week for application of the previously selected dose of DPCP to the whole scalp. Week 18 will only have one treatment application visit. Treatment visits must be at least 24 hours apart. The drug will be applied by trained a member of the MCRU and/or Dermatology clinical research staff. AEs will be recorded each visit (Appendix C) and will be monitored.

Investigator Assessment Visits (Weeks 4, 8, 12, and 16)

Every four weeks during treatment, the investigator will attend one of the treatment visits at the CRU or Dermatology Clinical Research to perform assessments of hair loss, including the SALT score and PAA, in addition to the regular treatments and data collection performed at every treatment visit. Photography will also be completed. Vital signs will be recorded and monitored at these visits. Pregnancy test will be administered to all women of childbearing potential once monthly at these visits. Laboratory tests related to safety monitoring will be drawn at week 12 of treatment.

Regrowth Sample Collection Visit

A visit will occur a minimum of 72-96 hours after a treatment visit in which the physician determines the subject has achieved a $\geq 50\%$ decrease in hair loss. Scalp biopsy and blood specimens will be collected. Vital signs and AEs (Appendix C) will be monitored and recorded. Handling of biopsy and blood specimens will follow the same protocol as was used at the Sensitization and Baseline Sample Collection Visit, Week 0. These samples will be obtained from an area of hair regrowth and ideally, in the same scalp region where the initial biopsy samples were obtained.

Follow-up Visit, Week 18

The follow-up visit will occur a minimum of 72-96 hours after the final application of the drug. The post-treatment scalp biopsy and blood specimens will be collected at this time. Vital signs and AEs (Appendix C) will be monitored and recorded. Laboratory test related to safety monitoring will be drawn at this time. Pregnancy test will be administered to all women of childbearing potential. No treatment will be provided. Handling of biopsy and blood specimens will follow the same protocol as was used at Week 0. Photography will be completed and assessments of hair loss, including the SALT score, the Physician Assessment of Alopecia (PAA; Appendix G), and the Subject Hair Loss Assessment (SHLA; Appendix H) will be done by the physician or subject.

Follow-up Visit, Week 20

Subjects will return to the CRU or Dermatology Clinical Research 10-14 days after the final biopsy collection procedure for suture removal. AEs (Appendix C) will be monitored and recorded. A Study Completion Form (Appendix J) will be completed by the investigator or study coordinator.

Early Termination Visit

If a participant withdraws from the study at any time between the Baseline/Sensitization Visit and the final week of treatment, the early termination visit should take place at the time of subject withdrawal. AEs (Appendix C) will be monitored and recorded. No treatment will be provided. The investigator will perform assessments of hair loss, including the SALT score and PAA. The subject will complete the final SHLA (Appendix H). Photography will also be completed. A Study Completion Form (Appendix J) will be completed by the investigator or study coordinator.

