	
from the study. (“Dose Determination Visit”; 10-14 days after the Sensitization Visit)
 
The subject will return 72 hours after the application of each dose (0.04, 0.08, 0.12, 0.2%) for an assessment by the PI or co-PI. As described above, the lowest dose will be applied first and assessed. If no reaction, the next lowest dose will be applied, etc, until adequate sensitization is attained. The weakest strength concentration that caused a minimal reaction will be used throughout the study. Once adequate sensitization has been obtained, 0.75-1 g of the treatment drug in that dose will be applied in a thin film that covers the entire scalp.
 
The treatment drug will be applied by the PI, a trained study coordinator, or a staff member of the Clinical Research Unit at the University of Minnesota. Eligible subjects may begin receiving the study drug immediately after enrollment and screening.
 
The estimated duration of the study is 22-24 weeks. See Appendix A for the schedule of visits. There will be a total of 42 scheduled visits, beginning with a screening visit followed by a single sensitizing dose of study drug at baseline (Day -16) and an initial dose determination application of 0.04% DPCP at Day -2. Additional visits could include another sensitization attempt as well as dose determination visits for the .04, 08, 0.12, and 0.2% DPCP.
 
Subjects will undergo twice weekly (+/- 2 days) topical applications of an ointment formulation of DPCP during Weeks 1-18. Application will be done twice per week. The drug application will be performed by a board certified dermatologist for the first two treatment visits (Days 0 and 3; Visits 4 and 5), after which a trained member of the Clinical Research Unit staff or a trained study coordinator will apply the drug twice each week (Weeks 2-18; Visits 6-39). The investigator will attend one treatment visit in the Clinical Research Unit each month to evaluate the extent of hair loss and hair growth (Weeks 4, 8, 12, and 16).
 
Scalp biopsy specimen collection will be performed at baseline (Day -16, Visit 2), 72-96 hours after the first treatment (i.e., challenge) application (Day 2, Visit 5), 72-96 hours after the final application (Week 18 +3d, Visit 39) or during treatment when the study subject is determined to have achieved >=50% hair regrowth.
 
Three scalp biopsy samples will be collected by a board certified dermatologist. When possible, each sample will be taken from a balding area near an area with hair preferably in a non-androgen dependent site of the scalp. One of the three samples will be frozen in OCT for histologic examination and immunohistochemical studies. A second biopsy sample from an adjacent area will be placed in 10% buffered

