8.2 Exploratory Endpoints

To identify scalp skin biomarker profiles that characterize a response to DPCP treatment, enabling the future potential for predicting individual responses to treatment and the likelihood of a sustained response with the opportunity to study blood samples in the future if needed.

Subject assessment of hair loss/growth with the subject hair loss assessment and investigator assessment of the total SALT score.

Gene expression and histologic analysis (immunohistochemistry) on skin biopsy specimens will be done. mRNA will be prepared from skin samples stored frozen in RNA Later solution. Expression of cytokine genes that define different polar sets of T-cells will be measured: interferon-gamma, IL-13, IL-17A, IL-22, IL-9, IL-32; other inflammation associated genes such as IL-12, IL-23, IL-1B, and IL-15 will also be measured. mRNAs for a series of negative immune regulatory genes, e.g., Foxp3, CTLA4, PD-1, etc. will be measured by RT-PCR. Re-initiation of hair growth will be assessed by measuring expression of mRNAs encoding hair-associated keratins and keratin-associated proteins. A subset of patients showing good responses of hair re-growth will be selected for whole transcriptome analysis. Pre and post-treatment lesional biopsies will have global mRNA profiles established using Affymetrix U133 2.0Plus arrays. From frozen samples in OCT blocks, frozen sections will be prepared that will be stained initially with antibodies to T-cells (CD3, CD8), dermal dendritic cells (CD11c), and the regulatory marker Foxp3. Once the gene expression analysis is completed, expression of negative immune regulatory proteins will be examined, as guided by the genes with highest up-regulation in post-treatment samples in patients with good hair regrowth.

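### The late biopsy of a subject with at least 50% regrowth is taken where hair has regrown, so its keratin and marker changes partly reflect the choice of spot

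*Combined protocol and SAP*

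**What the plan says.** The protocol describes the biopsy site in several places.

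- **Study Summary, Study Design.** When possible, "each sample will be taken from a balding area near an area with hair preferably in a non-androgen dependent site of the scalp". The late biopsy follows the final application, "or during treatment when the study subject is determined to have achieved >=50% hair regrowth".
- **Section 3.1, Sensitization and Baseline Sample Collection Visit.** "Three 4-mm scalp biopsy samples will be collected from perilesional scalp", with the remark that in some patients this may be beside only a few tufts.
- **Section 3.1, Day 3 visit.** The second set is taken about 2 inches from the first.
- **Section 3.1, Regrowth Sample Collection Visit.** Once the physician judges that hair loss has fallen by at least 50%, "These samples will be obtained from an area of hair regrowth"; matching the region of the first biopsies is only the ideal.
- **Section 3.1, Follow-up Visit, Week 18 (Visit 41).** No site is named. Only specimen handling is tied to Week 0.
- **Section 8.2.** "Pre and post-treatment lesional biopsies will have global mRNA profiles established", in a subset of good responders. Also: "Re-initiation of hair growth will be assessed by measuring expression of mRNAs encoding hair-associated keratins".
- **Appendix A, notes c and d.** The third set is taken at regrowth or at Visit 41, as alternatives.

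Section 2 sets the exploratory aim as the association of cytokine and keratin profiles and ULBP expression with hair regrowth. Section 10.2 plans confidence intervals and paired t-tests on changes in T-cell and dendritic-cell markers. It has no term for biopsy site.

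**The concern.** The regrowth visit is triggered by a 50% fall in hair loss, the same threshold as SALT50, the second-ranked primary endpoint. Reaching it changes where on the scalp the late sample is taken. A transcript that differs between regrown and balding skin of the same person can then appear as a treatment change in these subjects because of where the punch was placed.

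Hair keratins are the most exposed. They serve as the tissue sign of renewed growth, and the aim is to relate them to regrowth, in samples selected because hair has regrown there. T-cell, dendritic-cell and cytokine markers may be exposed too. The Introduction reports higher T-cell and dendritic-cell markers in a subset of lesional samples, and the Cytokine Profiling section reports transcriptome differences between lesional and non-lesional areas. Neither statement concerns regrown scalp as such, so for these markers the effect is plausible but not shown.

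The selection also carries forward. Section 8.2 chooses the regulatory proteins to examine from the genes most up-regulated in post-treatment samples of subjects with good regrowth.

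**Working it through.** **1. Site by sample.**

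- Baseline: perilesional (section 3.1); balding near hair when possible (Study Summary).
- Day 3: about 2 inches from baseline.
- Late set, subject with at least 50% regrowth: regrown area.
- Late set, anyone else: not stated at the visit. Only the Study Summary's general rule is available.
- Section 8.2: lesional before and after.

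A spot chosen because hair has regrown does not fit the general rule or the word lesional.

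**2. Is there a still-balding comparator?** Under Appendix A notes c and d, a subject sampled at regrowth has no further set, and section 3.1 also links the two occasions with *or*. The Week 18 text and the section 3.1 visit table mark the Visit 41 biopsy without that condition, so this needs reconciling too. A second sample, if taken, would still have no stated site.

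**3. Is the choice of spot a real choice at the trigger?** Entry SALT is 76 to 99. A fall of at least 50% leaves at most 0.5 × 76 = 38 to 0.5 × 99 = 49.5; from 90, at most 45. A subject who has just met the trigger therefore still has substantial bald scalp. This shows that selection is possible. It does not measure its effect.

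**4. The plan's own biomarker figures.** The log10 SD is not given, but section 10.2 gives confidence-interval widths of 46-fold (n = 6) and 20-fold (n = 8). From width = 10^(2 × t × SD / √n):

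- n = 6: SD = log10(46) × √6 / (2 × 2.571) = 0.792
- n = 8: SD = log10(20) × √8 / (2 × 2.365) = 0.778

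Exact noncentral-t power of 80% at two-sided 0.05 needs a standardised change of 1.435 (n = 6) or 1.156 (n = 8). The detectable changes are 10^(1.435 × 0.79) = 13.6-fold and 10^(1.156 × 0.78) = 8.0-fold, which agree with the 14-fold and 8-fold in the Study Summary. (Section 10.2 gives 14-fold for both sizes; that is a separate matter.)

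**5. Illustration only.** Assume no true change, SD 0.785, every subject sampled at regrowth, and a pure regrown-versus-balding ratio F. The documents give no F. The noncentrality is √n × log10(F) / 0.785. The chance that the paired t-test is significant, against a nominal 0.05, is:

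- F = 2: 0.120 (n = 6), 0.156 (n = 8)
- F = 5: 0.423, 0.582
- F = 10: 0.705, 0.869

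If k of n subjects are sampled at regrowth, the spurious mean change is F^(k/n). At one half this is √F, or 1.41-, 2.24- and 3.16-fold. The range shows that the result depends on an unknown F and on how many subjects reach the trigger.

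**The case against.** The strongest reply is that regrown tissue is a legitimate target. With 76% to 99% loss at entry, an area of regrowth is largely scalp that was bald and recovered, and bald-to-regrown in the same region is the local change the study wants to describe. A spot chosen without regard to regrowth might miss it, with only 6 to 8 evaluable subjects expected. This stands. It supports keeping such samples as description, but not reading them as evidence of association.

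Keratin would also track hair at the sampled spot under any site rule. True, but selecting the spot for regrowth makes the overlap nearly complete.

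Several stronger readings are tempting, and the documents do not support them:

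- *Responders give bald-versus-haired pairs and non-responders bald-versus-bald.* The Week 18 visit names no site, the general rule is qualified by when possible, and baseline is perilesional. The second half is inference.
- *A responder-versus-non-responder test is biased.* No such test is specified. The stated test is paired pre/post, and the whole-transcriptome work is confined to good responders.
- *The whole exploratory aim is circular.* Baseline and Day 3 samples precede the outcome, so predictors of response drawn from them escape this rule. Blood has no scalp site.
- *Hair status can never be recovered.* An adjacent formalin specimen is assessed for follicle differentiation, and regrowth-visit samples are regrown by rule. Recovery is partial, though, and nothing requires the status or exact location to be recorded.

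**Conclusion.** The point holds in limited form. For subjects sampled at regrowth, the pre/post change in hair keratins, and possibly in T-cell, dendritic-cell and cytokine markers, is partly selected by the site rule, and the planned analysis has no means of separating the two. Using keratin expression in those samples to support an association with regrowth is largely circular.

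The size of the bias cannot be computed from the documents. A reader might take the SALT arithmetic or the error rates above as an estimate. They are not one: the first shows only that bald scalp remains, and the second rests on an assumed F and on every subject being sampled at regrowth.

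The conclusion assumes that the regrowth-visit instruction is followed as written and that Appendix A's either/or governs the third set. It concerns an exploratory endpoint. The SALT endpoints are untouched, and no sample size or power figure changes. It is still worth correcting before sampling, because it limits what the exploratory aim can conclude and the remedy is nearly free.

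**What to change.** 1. Reconcile the Study Summary, the baseline, regrowth and Week 18 paragraphs of section 3.1, and section 8.2 on the site of the late biopsy. State the site for Visit 41, including for subjects with less than 50% regrowth and those first reaching 50% at that visit. Make clear whether a subject sampled at regrowth is sampled again.
2. Record on the CRF, for every sampled spot, whether it is haired, regrown or bald, and its location relative to the baseline site. The Day 3 instruction already specifies a distance.
3. Report the paired marker changes by that status.
4. If regrown-area sampling is kept, call those samples regrown rather than lesional, treat their changes as descriptive, and do not use their keratin levels as evidence of an association with regrowth.

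Moving these biopsies to a spot chosen without regard to regrowth is an option with a real loss, and is not needed for the steps above.

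Cost: revised wording and one CRF field, with no extra biopsy. The subgroups by hair status will be very small, and the exploratory conclusion on keratins will be narrower.
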